10.5 Radiological Imaging and Non-pharmacologic Treatment/Procedures

Chest x-rays and CT scan of the chest will be recorded on the study eCRF. Surgeries and non-pharmacologic procedures of interest performed in accordance with routine standard of care will be recorded on the study eCRF. Surgeries of interest include surgeries of the chest and chest wall, such as pleural tube placement and video assisted thoracoscopic surgery.

10.6 Clinical Efficacy Outcomes Assessments Time Points

Clinical outcomes assessments will be performed by a blinded investigator at the study site. At each time point, the site blinded investigator will evaluate signs and symptoms and record physical findings of CABP. These assessments will include cough, difficulty breathing, purulent sputum production, chest pain, grunting, hypotension, tachycardia, tachypnea, and evidence of pulmonary consolidation (further details are in the Blinded Investigator Plan). If symptoms and physical exam findings are available in the medical record per standard of care, these can be used for the clinical outcomes assessments.

Clinical efficacy outcomes assessments will be performed at the following time points:

- A baseline assessment of signs, symptoms, and physical exam findings will be completed at screening
- Clinical improvement on the last day of treatment (+48 hours) (primary efficacy endpoint)
- Clinical improvement on Day 3 or 4. If the subject is discharged from the hospital prior to Day 3, assessment may be recorded on Day 2. A return visit is not required to perform this assessment if the subject has been discharged prior to the assessment.
- Clinical cure during SFU at 16 days (+/-4 days) post-randomization (secondary efficacy endpoint). This assessment will be conducted if information is available per standard of care and may be recorded from the medical record via phone/other media.

10.7 Clinical Improvement Definition (Early Clinical Response and End-of-Treatment Response)

Clinical improvement is defined as improvement of at least 1 of the presenting signs and symptoms of CABP with no deterioration in any presenting sign or symptom of CABP, no development of new sign or symptom of CABP, and no requirement for additional or alternative antimicrobial therapy.

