7 STUDY DESIGN

This is a phase 2/3, randomized, open-label, active-control, multi-center study to assess the safety and efficacy of solithromycin in children and adolescents with CABP. Approximately 400 subjects (~300 in the solithromycin group and ~100 in the comparator group) will be enrolled. Randomization will be stratified by age group (12 through 17 yo, 6 to <12 yo, 2 to <6 yo, and 2 months to <2 yo). At least 40 subjects will be randomized into each age group.

Subjects who meet all inclusion/exclusion criteria and sign the informed consent/assent will be enrolled. Subjects will be randomized to receive solithromycin or a comparator antibiotic, administered IV and/or by mouth (PO) based on weight and age. Subjects will be treated daily for 5 to 7 days with oral solithromycin and 5 to 7 days with IV or IV-to-oral solithromycin. Subjects will be treated for 5 to 10 days with comparator antibiotics. Subjects will have safety and efficacy assessments during and after treatment.

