7.3 Study Drug Dosage and Administration

Solithromycin will be administered IV or PO according to Table 5 through Table 8 below. If dosing begins with oral therapy, the Day 1 dose will be a loading dose. No loading doses are used with IV solithromycin administration or if switched to oral administration. An IV-to-PO switch can occur after the first IV dose. Subjects starting with oral therapy will receive 5 days of solithromycin treatment, and those starting with IV therapy (regardless of if and when they switch to oral therapy), will receive 7 days of solithromycin treatment.

For subjects receiving the capsule formulation, 200 mg solithromycin capsules will be used to provide the absolute dose of either 200 mg, 400 mg, or 800 mg. The capsule dose will be rounded upwards to the nearest 200 mg, not to exceed an 800 mg loading dose and 400 mg maintenance dose. Study drug should be swallowed with water approximately every 24 hours and at approximately the same time each day (± 4 hours). Study drug can be taken without regard to food.

Table 5 Capsule Dosing Regimens

Age (years)	Weight	Route	Formulation	Day 1 (Max dose: 800 mg)	Days 2 to 5 (Max dose: 400 mg)
6 to 17	>30 kg	PO	Capsules	800 mg	400 mg
	>20 to 30 kg	PO	Capsules	600 mg	400 mg
	≤ 20 kg	PO	Capsules	400 mg	200 mg

Subjects requiring an oral dosage form other than capsules will receive suspension formulation, provided at 275 mg/5 mL strengths, to achieve the age-appropriate mg/mL and solithromycin dose. Any dosing variations within 10% of the calculated suspension dose is not considered a deviation.

Table 6 Suspension Dosing Regimens

Age (years)	Route	Formulation	Day 1 (Max dose: 800 mg)	Days 2 to 5 (Max dose: 400 mg)
12 to 17	PO	Suspension	20 mg/kg (800 mg)	10 mg/kg (400 mg)
6 to <12	PO	Suspension	20 mg/kg	10 mg/kg
2 to <6	PO	Suspension	20 mg/kg	10 mg/kg
2 mo to <2	PO	Suspension	20 mg/kg	10 mg/kg

No loading doses are used with IV solithromycin administration. Intravenous solithromycin should be infused over approximately 60 minutes (± 20 minutes) approximately every 24 hours (± 4 hours). Changes to the infusion duration should be discussed with the study medical monitor prior to study drug administration. Any dosing variations within 10% of the calculated IV dose is not considered a deviation.

Table 7 Intravenous Dosing Regimens

Age (years)	Route	Formulation	Days 1 to 7 (Maximum dose: 400 mg)
12 to 17	IV	Solution	8 mg/kg
6 to <12	IV	Solution	8 mg/kg
2 to <6	IV	Solution	8 mg/kg

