Ampicillin	150-200 mg/kg/day intravenously in equally divided doses every 6 hours	-
Azithromycin	10 mg/kg intravenously/orally on day 1 [500 mg maximum dose] followed by 5 mg/kg orally every 24 hours [250 mg maximum dose]	10 mg/kg orally on day 1 [500 mg maximum dose] followed by 5 mg/kg orally every 24 hours [250 mg maximum dose]
Ceftriaxone	50-75 mg/kg/day intravenously in equally divided doses every 12 hours; total daily dose should not exceed 2 g	50-80 mg/kg intravenously once daily
Erythromycin	40 mg/kg/day orally every 6 hours	30-50 mg/kg/day orally every 6 hours
Erythromycin lactobionate	15 to 20 mg/kg/day intravenously in equally divided doses every 6 hours	50 mg/kg/day intravenously/orally in equally divided doses every 6 hours

Note: if doses of comparator drugs noted in the dosing table above differ those prescribed per standard of care, a site can use the locally prescribed dose.

IV-to-PO switch:

Subjects receiving an IV comparator drug (i.e., ceftriaxone, ampicillin) in any age group may be switched to oral treatment using amoxicillin-clavulanic acid PO (amoxicillin component, 45 mg/kg every 12 hours; subjects weighing ≥40 kg, 875 mg every 12 hours or 500 mg every 8 hours) or amoxicillin alone (45 mg/kg every 12 hours, up to a maximum of 4 g/day).

Subjects must receive 5 to 10 days of treatment with comparator. The exact duration of treatment may be determined at the investigator's discretion.

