10.8 Clinical Cure Definition (Day 16 Post Randomization [±4 Days])

Clinical cure is defined as resolution of all presenting signs and symptoms of CABP (excluding cough), no development of new sign or symptoms of CABP, and no requirement for alternative antimicrobial therapy.

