10.4 Secondary Efficacy/Clinical Outcomes

Evaluation of clinical signs and symptoms of CABP, requirement for additional or alternative antimicrobial therapy, and efficacy will be performed by a blinded investigator or designee at the site. Outcomes will be assessed at the following time points:

- Baseline clinical signs and symptoms assessment
- Clinical improvement on Day 3 - 4. If the subject is discharged from the hospital prior to Day 3, assessment may be recorded on Day 2.
- Clinical improvement on the last day of treatment (+48 hours)
- Clinical cure during short-term follow up at 16 days (\pm 4 days) after randomization (secondary efficacy endpoint). This assessment will be conducted if information is available per standard of care and may be recorded from the medical record via phone or other media.

Efficacy will be quantified as a binary variable at each timepoint listed above using the algorithm specified in Appendix 2. Clinical improvement is defined as improvement (compared to baseline) of at least 1 of the presenting signs and symptoms of CABP with no deterioration in any presenting sign or symptom of CABP (compared to baseline), no development of new sign or symptom of CABP, and no requirement for additional or alternative antimicrobial therapy. Clinical cure is defined as resolution of all presenting signs and symptoms of CABP (excluding cough), no development of new sign or symptoms of CABP, and no requirement for additional antimicrobial therapy. Clinical improvement and cure will be determined using the specific signs and symptoms data recorded on the eCRF, as well as a separate question on the eCRF concerning additional antimicrobial therapy. These questions will be completed by the blinded investigator (or potentially unblinded investigator in the case of screening evaluation), who will be supplied with information according to the blinded investigator plan.

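### Antibiotics continued past Day 5 or 7 can fail a solithromycin child at end of treatment, but up to Day 10 they belong to the comparator's assigned course

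*Protocol*

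**What the plan says.** **Course length.** Protocol 7.3 gives solithromycin a set length by starting route: "Subjects starting with oral therapy will receive 5 days of solithromycin treatment", and those who start IV "will receive 7 days of solithromycin treatment". For the other arm, "Subjects must receive 5 to 10 days of treatment with comparator", with the exact length left to the investigator. SAP 3.1 and 3.4 repeat both rules. Protocol Section 7 still carries different text: "Subjects will be treated daily for 5 to 7 days with oral solithromycin and 5 to 7 days with IV or IV-to-oral solithromycin". That passage and 7.3 must be reconciled. On either text the solithromycin maximum is 7 days and the comparator maximum is 10.

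**Endpoint rule.** Protocol 10.7 defines improvement, for both early response and end of treatment, as at least one presenting sign or symptom better, none worse, and "no development of new sign or symptom of CABP, and no requirement for additional or alternative antimicrobial therapy". SAP 10.4 repeats "no requirement for additional or alternative antimicrobial therapy". The end-of-treatment reading is taken on the last day of treatment or within 48 hours after it (Protocol 10.6).

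**Day 16 cure.** Protocol 10.8 ends with "and no requirement for alternative antimicrobial therapy". The cure sentence in SAP 10.4 disqualifies *additional* therapy instead.

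**Scoring and reporting.** SAP 10.4 scores each time point by an algorithm in Appendix 2, using the recorded signs and a separate eCRF question on additional antimicrobials. Table 14.5.1 is the only efficacy table, by arm and consolidated age group.

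**The concern.** One clinical judgement, that a child should stay on antibiotics a few days longer, is recorded differently in the two arms. On solithromycin it can be met only with a drug outside the assigned regimen, which is the event the endpoint counts as failure. On comparator it is met by continuing the assigned drug, and the child is assessed when that longer course ends. The antimicrobial component therefore partly measures how much room each regimen leaves for extension.

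Blinding the outcome assessor does not remove this, because the treating investigator, who knows the arm, decides whether antibiotics continue. The response rates appear side by side by arm, so a reader could take the difference as one of drug effect.

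**Working it through.** **The same decision in each arm, on the visible text**

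| | Solithromycin | Comparator |
|---|---|---|
| Assigned course | 5 days (oral start) or 7 days (IV start) | 5 to 10 days, investigator's choice |
| End-of-treatment reading | Day 5-7 or Day 7-9 | Day 5 to Day 12 |
| Antibiotic wanted after Day 5 or 7 | non-study drug | assigned drug, up to Day 10 |
| Improvement at end of treatment | lost, if the need is known by the visit | not affected |
| Early response (Day 3-4) | not affected | not affected |

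The reading windows are the course lengths plus 48 hours.

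**Does another rule correct this?** SAP 3.4 has failure rules for drug changes on comparator only. An IV-to-oral switch to a different drug is not a failure unless the site records premature discontinuation, and the same-formulation change rule is limited to the first 5 days. There is no parallel rule for a solithromycin child moved to another antibiotic. SAP Section 9 summarises days of study drug. Table 14.4.7 lists concomitant medications by generic name. Neither shows total antibacterial days by arm.

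**Day 16 cure.** After a completed course, a follow-on drug may or may not be *alternative* (Protocol) or *additional* (SAP). The documents do not settle it.

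**Size.** The plan states no figure for an efficacy comparison. Its sample size rests on safety, and that figure reproduces: 1 - 0.99^300 = 0.951, against 0.95 in Protocol Table 11.

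Assumed inputs, not in the documents: 90% of children in each arm would be scored successes apart from this component, and a share s is judged to need antibiotics past the solithromycin course. Let o be the share of all children who are both extended and would fail anyway. Then:

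- artefact = -(s - o)
- independence: o = 0.10 × s, so artefact = -0.90 × s
- greatest overlap: o is the smaller of s and 0.10
- 95% half-width under independence = 1.96 × √[p₁(1 - p₁)/n₁ + 0.90 × 0.10/n₂], with p₁ = 0.90(1 - s)

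| s | p₁ | Artefact, independent | Artefact, greatest overlap | Half-width 300:100 | Half-width 75:25 |
|---|---|---|---|---|---|
| 5% | 0.855 | -4.5 | 0 | 7.1 | 14.2 |
| 10% | 0.810 | -9.0 | 0 | 7.4 | 14.7 |
| 15% | 0.765 | -13.5 | -5.0 | 7.6 | 15.2 |

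All artefacts and half-widths are in percentage points. For s = 10% at 300:100: √(0.1539/300 + 0.09/100) = 0.0376, and 1.96 × 0.0376 = 0.074. At s = 15% the artefact cannot reach 0, because only 10% of children fail otherwise. Independence is taken as the outer case, since a wish for more antibiotics is likelier in a child who is doing badly.

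SAP Section 2 puts final enrolment below one quarter of 400, that is below 100. The 75:25 column is therefore a best case for precision.

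**The case against.** **The deciding rule may be elsewhere.** SAP Appendix 2 and the Blinded Investigator Plan were not in the text available. Either could define additional therapy so that the asymmetry disappears. This stands, and the point is limited to the visible text.

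**It is partly a choice of what to estimate.** The solithromycin durations were deliberately matched to the adult regimens (Protocol 5.4). Needing another drug after the full regimen can fairly count as failure of that regimen. This also stands, and is why the protocol definitions should remain the main rule. It does not tell the reader how much of an observed difference comes from this component.

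**Two stronger readings are tempting and are not supported.**

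- A reader might infer that the same slow response is failure in one arm and success in the other. One improved sign with none worse or new is enough in both arms. Only the decision to continue antibiotics triggers the rule.
- A reader might infer that the artefact would look like clear inferiority. No between-arm test, margin or interval is planned, only exact intervals per arm, and both documents say efficacy is not powered for comparison. Even at 300:100 with 10% extension and underlying success of 80% to 90%, a two-sided 5% test would be significant with probability only 0.34 to 0.56.

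**Some exposure data are already reported.** Days of study drug and concomitant medications are tabulated by arm. They are in separate tables and cannot be combined per child from the planned outputs.

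**Conclusion.** The asymmetry holds on the plain reading for end-of-treatment improvement. It does not touch early response. For Day 16 cure it is open until the *alternative* and *additional* wordings are reconciled.

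The direction is against solithromycin, but the size is unknown. Under the assumed 90% success, the artefact can be 0 for extension rates up to 10%, and reaches -4.5 to -13.5 points at 5% to 15% extension if extension is independent of response. At the enrolment reached, every one of these values is smaller than the half-width of about 14 to 15 points.

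The consequence is limited to how the descriptive rates by arm are read. Efficacy is secondary here and is extrapolated from adults. A supportive table is worth having because a small sample does not remove a directional scoring effect, and a few extended courses could visibly move the rates.

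**What to change.** Keep the protocol definitions as the main rule. Make the cure wording the same in Protocol 10.8 and SAP 10.4; with enrolment closed, the practical place to state which governs is the SAP. If Appendix 2 already scores extension alike in both arms, say so in SAP 10.4.

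Add to SAP 10.4 and Table 14.5.1, by arm:

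1. The number failing solely on the antimicrobial component, with the study day on which the non-assigned drug started.
2. Total days of any systemic antibacterial, assigned or not, through Day 16.
3. One supportive improvement rate and one supportive cure rate in which any systemic antibacterial after one common study day, for example Day 7, is scored identically in both arms. Show it once as failure and once as not failure, and label the two results as bounds. Do not set the day by comparator route, because SAP 5.1 declines to classify comparator children by route.

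Cost: SAP wording and one descriptive table. Protocol 8.3 and Table 1 footnote q call for antibiotic recording through follow-up, but the Day 16 visit list (10.3.1) has no medication review, so check completeness first. The failure bound also counts planned comparator courses past the common day. The not-failure bound can count a rescued child as a success. With Day 7, a replacement started on Day 6 or 7 after a 5-day oral course stays under the protocol rule; item 1 shows how many there are.

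This changes scoring and reporting only, not treatment length.

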10.8 Clinical Cure Definition (Day 16 Post Randomization [±4 Days])

Clinical cure is defined as resolution of all presenting signs and symptoms of CABP (excluding cough), no development of new sign or symptoms of CABP, and no requirement for alternative antimicrobial therapy.

10.9 Signs and Symptoms of CABP

- Cough
- Difficulty breathing
- Production of purulent sputum
- Chest pain
- Grunting
- Hypotension
- Tachycardia defined as follows:
 - 2 months to <24 months: ≥ 160 beats/min
 - 24 months to <10 years: ≥ 140 beats/min
 - ≥ 10 years: ≥ 100 beats/min
- Tachypnea, defined as follows:
 - 2 months to <12 months: ≥ 50 breaths/min
 - 12 months to <5 years: ≥ 40 breaths/min
 - ≥ 5 years: ≥ 20 breaths/min
- Physical exam consistent with pulmonary consolidation

11 STUDY AND SUBJECT DISCONTINUATION

A clear distinction will be made between subjects who discontinue study drug dosing and those who withdraw or are withdrawn from the study. Only those subjects who are lost to follow-up, are unwilling to comply with protocol procedures, or who withdraw consent and/or refuse any further contact with respect to the study will be withdrawn from the study. Subjects discontinued from study drug dosing and/or withdrawn for the study will not be replaced, regardless of the reason.

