11.3 Withdrawal from Study

A subject may be withdrawn from the study for any of the following reasons:

- Subject wishes to withdraw consent for reasons other than an adverse experience
- Subject wishes to withdraw consent due to an adverse experience
- Subject is lost to follow-up
- Subject non-compliance or unwillingness to comply with the procedures required by the protocol
- Investigator discretion
- Sponsor request

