5.4 Handling of Missing Data

Efforts will be made to minimize the occurrence of missing data. However, the general approach will be to use only data which are complete with regard to the variable(s) and timepoint(s) being analyzed for descriptive summaries, or for the evaluation of safety and efficacy endpoints. In the case of a patient withdrawing or being lost (unrelated to documented AE or SAE), the denominator for rates of AE and SAE occurrence will remain as the complete Safety Population.

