6 ANALYSIS POPULATIONS

Randomized population: All subjects who were enrolled and randomized in the study will be included in the analysis population for evaluating efficacy. This population will be used for analyses of efficacy.

Safety population: All subjects who receive at least one dose of study drug (solithromycin or active comparator) will be included in the analysis population for evaluating safety. This population will be used for analyses of safety.

PK population: All subjects who receive at least one dose of solithromycin (regardless of randomization assignment) and had at least one evaluable PK sample will be included in the analysis population for evaluating PK.

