10.2 Primary Safety and Tolerability Endpoints

Primary safety endpoints will be the proportion of subjects in the safety population experiencing a TEAE and the proportion of subjects in the safety population discontinuing study drug due to a related AE. Discontinuation from related AE counts will be created by using any discontinuation from related AE documented in the study drug discontinuation page and the AE data for a subject. The first safety endpoint will be evaluated through the Day 28 visit (28 days ± 4 days after randomization). This will be a composite of TEAEs through Day 16 visit and TESAEs through Day 28 visit. The second safety endpoint will be evaluated through the last day of study drug dosing.

For the primary safety end points, the frequency and percentage of subjects with at least one treatment emergent adverse event, and the frequency and percentage of subjects discontinuing study drug due to a related AE, will be determined. Ninety-five percent Clopper-Pearson (exact) confidence intervals will be calculated for each incidence of occurrence by treatment arm. Summaries will be calculated by treatment arm for the overall safety population, by treatment arm stratified within age group, and within age group and formulation for the solithromycin arm. Patient-level information for adverse events and subjects discontinuing study drug due to a related AE will be listed. For this analysis subjects will be grouped according to their randomized treatment arm assignment (intent-to-treat analysis).

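### Protocol 11 and 11.3 disagree on who may be withdrawn from the study; following 11.3 can end safety follow-up early, and the SAP's full-denominator rule would then let the first primary safety proportion be understated

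*Protocol*

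**What the plan says.** Protocol 11 undertakes to keep stopping study drug separate from leaving the study, and gives a closed list for the latter: "Only those subjects who are lost to follow-up, are unwilling to comply with protocol procedures, or who withdraw consent and/or refuse any further contact". Protocol 11.3 opens differently, with "A subject may be withdrawn from the study for any of the following reasons", and names six reasons. Four of them fit the closed list: two forms of consent withdrawal, loss to follow-up, and non-compliance. The other two, "Investigator discretion" and "Sponsor request", do not. Both also appear in Protocol 11.2 as reasons for stopping study drug. Section 11.2 adds that a child who stops drug early should be encouraged to stay in the study to the last visit.

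On the analysis side, SAP 6 fixes the denominator: "All subjects who receive at least one dose of study drug (solithromycin or active comparator) will be included in the analysis population for evaluating safety". SAP 10.2 sets the first primary endpoint on it: "Primary safety endpoints will be the proportion of subjects in the safety population experiencing a TEAE", counting TEAEs to the Day 16 visit and serious ones to the Day 28 visit, with an exact interval by arm. SAP 5.4 says that when a patient withdraws or is lost for a reason not tied to a documented event, "the denominator for rates of AE and SAE occurrence will remain as the complete Safety Population". No time-at-risk or sensitivity analysis of this proportion is listed.

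**The concern.** A site reading Section 11 would keep following a child whose family is willing and reachable. A site reading 11.3 could end that child's study participation at the investigator's or sponsor's initiative. Under the second reading, events after that date are not collected, but the child still counts in the denominator of a simple proportion. If no TEAE had been recorded by then, the unobserved days are in effect scored as no event.

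This matters because safety is the primary objective and the endpoint is a cumulative proportion over a fixed window. Any error from this source lowers the proportion. Treatment is open-label and only the efficacy assessor is blinded (Protocol 9.6), so whoever exercises the discretion knows the arm.

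**Working it through.** **1. The passages side by side.**

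| Reason for leaving the study | Protocol 11 | Protocol 11.3 | Also a reason to stop drug (11.2) |
|---|---|---|---|
| Lost to follow-up | yes | yes | no |
| Unwilling to comply | yes | yes | yes |
| Consent withdrawn or contact refused | yes | yes | yes, if not for an adverse experience |
| Investigator discretion | no | yes | yes |
| Sponsor request | no | yes | yes |

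All of this is current text, not the amendment log. The last two rows conflict.

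**2. The plan's own figure.** The sample size rests on the chance of seeing at least one serious event at 1% incidence with n=300: 1 − 0.99^300 = 0.951, against 0.95 stated. It reproduces. SAP 3.3 says that it assumes all 300 are evaluable for safety.

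**3. Size of a possible shortfall in the first primary endpoint.** The documents give neither a withdrawal rate nor an expected pediatric TEAE rate, so these are assumptions:
- a 36% TEAE proportion by Day 16, at constant hazard;
- a share w of dosed children withdrawn at day d, for reasons unrelated to adverse-event risk;
- no events recorded after withdrawal.

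Daily hazard: h = −ln(1 − 0.36)/16 = 0.0279.

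Shortfall = w × [exp(−h·d) − exp(−16h)].
- d = 3: 0.9197 − 0.6400 = 0.2797
- d = 5: 0.8698 − 0.6400 = 0.2298

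| w | withdrawn at Day 3 | withdrawn at Day 5 |
|---|---|---|
| 2% | 0.6 points | 0.5 points |
| 5% | 1.4 points | 1.1 points |
| 10% | 2.8 points | 2.3 points |

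**4. Against sampling error.** SE = sqrt(0.36 × 0.64/n), which is 5.5 points at n=75 and 2.8 at n=300. SAP 2 says that fewer than a quarter of the planned 400 were enrolled, so under 3:1 allocation 75 is about the most the solithromycin arm can hold. At w = 5% and Day 3, the shortfall is 1.4/5.5, about a quarter of an SE at n=75, and 1.4/2.8, half an SE at n=300.

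**5. Wider ranges.** More generally the shortfall is p × w × m, where p is the true TEAE proportion and m is the share of withdrawn children's would-be first events that fall after withdrawal. For p = 30% and w = 5%, it is 0 at m = 0, 0.75 points at m = 0.5 and 1.5 points at m = 1. The extreme of the ranges tried (p = 50%, w = 10%, m = 1) gives 5 points. The probability in step 2 falls from 0.951 to 0.943 at w = 5% and to 0.934 at w = 10%, with m = 1.

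**6. What excluding withdrawn children would do.** Take 36%, w = 5%, Day 3. The recorded proportion is 0.360 − 0.014 = 0.346. The event-free withdrawn share is 0.05 × 0.9197 = 0.046.
- Dropping those children gives 0.346/0.954 = 36.3%, slightly above the true 36%.
- Counting them all as events gives 0.346 + 0.046 = 39.2%, an upper bound.

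**7. The second primary endpoint.** Discontinuation for a related event is assessed only to the last day of dosing (SAP 10.2), so follow-up lost after that day hardly touches it.

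**The case against.** The strongest reply is that the conflict in Section 11 does not cause the analysis problem. SAP 5.4 treats every unrelated withdrawal or loss alike, including those that Section 11 allows. Deleting two bullets from 11.3 would leave that rule in place. This stands: aligning the sections reduces only avoidable withdrawals.

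A reader might go further than the text allows in four ways.
- *That withdrawn children are analysed as event-free.* They are not. A TEAE recorded before withdrawal counts in full, and the 5.4 sentence does not cover withdrawals tied to a documented event. Only an unrecorded first TEAE after withdrawal is lost.
- *That the primary rate is understated.* No document shows a withdrawal for either disputed reason, so this remains a possibility.
- *That the March 2018 termination led to withdrawals at sponsor request.* SAP 2 reports the termination. It does not say that any child under follow-up was withdrawn or that event collection stopped.
- *That the bias differs by arm.* Open-label discretion makes this possible, but nothing in the documents shows it.

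Safeguards also exist. Stopping drug does not end follow-up (11.2). Protocol Table 1, note d, requires telephone collection when a child cannot or will not return, although 10.3.1 and 10.3.2 mention only serious events and none of these says that it covers a child already withdrawn from the study. SAP 7 already summarises the timing and reasons for withdrawal. Finally, SAP 1.1 postdates termination, so new protocol wording cannot recover data, and the analysis is descriptive. These points lower the weight of the concern. They do not resolve the contradiction or supply the missing sensitivity analysis.

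**Conclusion.** The contradiction is real and must be reconciled. If 11.3 is followed, the first primary safety proportion can be understated, and an error from this source can only be downward. Its size cannot be derived from the documents. The 0.5 to 2.8 points is conditional on an assumed 36% TEAE rate and on 2% to 10% of children being withdrawn at Day 3 to 5. At the enrolment reached, sampling error is larger than this. The point merits correction because it touches the primary endpoint and costs little, not because a material bias has been shown.

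**What to change.** **Protocol.** Reconcile 11.3 with the closed list in Section 11, so that a stop initiated by the investigator or sponsor is recorded as a drug discontinuation under 11.2 and not as an exit from the study. State that adverse-event contact then continues to Day 16 and serious-event contact to Day 28, by telephone where the child does not return, as Table 1, note d, already provides. This concerns data collection only and says nothing about when treatment should stop. For this terminated trial it comes too late to change what was collected.

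**SAP and report.** Keep the full-denominator analysis as the main one. From the withdrawal timing and reasons already summarised under SAP 7, report by arm how many children have incomplete safety follow-up. Add one sensitivity analysis of the TEAE proportion: either a Kaplan-Meier or other time-at-risk estimate, or a bound that counts event-free early withdrawals as events. Do not exclude those children, since that pushes the estimate upward. Also bring SAP 3.3, which contemplates leaving out a subject who withdrew consent before safety follow-up was complete, into line with SAP 5.4 and 6.

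**Cost.** A few lines of wording, one extra table, and a safety estimate that may be slightly less favourable or wider.
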